## 7.6. Drug Interactions

No formal drug-drug interaction studies with sacituzumab govitecan have been conducted. SN-38 (the active metabolite of sacituzumab govitecan) is metabolized via human *UGT1A1*. Concomitant administration of inhibitors or inducers of *UGT1A1* (Appendix 17.6), with sacituzumab govitecan, should be avoided because of the potential to either increase (inhibitors) or decrease (inducers) the exposure to SN-38, unless there are no therapeutic alternatives.

### 7.6.1. UGT1A1 Inhibitors

Co-administration of sacituzumab govitecan with inhibitors of *UGT1A1* may increase systemic exposure to the active metabolite, SN-38. Do not administer *UGT1A1* inhibitors with sacituzumab govitecan unless there are no therapeutic alternatives. A list of example UGT1A1 inhibitors is provided in Appendix 17.6.

### 7.6.2. UGT1A1 Inducers

Exposure to SN-38 may be substantially reduced in subjects concomitantly receiving *UGT1A1* enzyme inducers. Do not administer *UGT1A1* inducers with sacituzumab govitecan unless there are no therapeutic alternatives. A list of example UGT1A1 inducers is provided in Appendix 17.6.

## **8. STUDY DRUG MATERIALS AND MANAGEMENT**

### **8.1. Study Drug**

Sacituzumab govitecan is supplied as a sterile, off-white to yellowish lyophilized powder in single-dose glass vials. It is formulated in 2-(*N*-morpholino) ethane sulfonic acid buffer containing trehalose and polysorbate 80 and contains no preservatives. Following reconstitution, the concentration of sacituzumab govitecan is 10 mg/mL. The pH of the reconstituted solution is approximately 6.5.

### **8.2. Study Drug Packaging and Labeling**

Sacituzumab govitecan is packaged in single-use, 50R, glass vials, closed with coated elastomeric stoppers and capped with flip-off caps with aluminum over seals. Study drug to be distributed to centers in the US and other participating countries shall be labeled to meet applicable requirements of the US Food and Drug Administration (FDA), European Union (EU) Guideline to Good Manufacturing Practice—Annex 13 (Investigational Medicinal Products), and/or other local regulations.

### **8.3. Study Drug Storage**

The glass vials of sacituzumab govitecan must be stored under refrigeration (2-8 °C) and protected from light until use. Since the formulated drug product contains no preservative, vials should be used only once. Refer to the current version of the Pharmacy Manual for additional details.

### **8.4. Study Drug Preparation**

Calculate the prescribed dose in mg based on the subject's body weight at enrollment (C1D1) (unless there is a > 10% change in body weight from enrollment or if required by institutional policy). Calculate the number of vials required for a dose, based on maximum concentration of 10 mg/mL after reconstitution.

The Pharmacist is required to follow the appropriate steps regarding the reconstitution and dilution of the drug product per the Pharmacy Manual.

### **8.5. Administration**

Do not administer as an IV push or bolus. Sacituzumab govitecan is administered via IV infusion as described below with additional information available in the current version of the Pharmacy Manual.

- Administer the **first** infusion over 3 hours ( $\pm$ 15 minutes). Subsequent infusions may be administered over 1 to 2 hours if previous infusions were well tolerated. Monitor the subject during the infusion, and for at least 30 minutes after infusion.

## 9. ASSESSMENT OF EFFICACY

CT or MRI scans with IV contrast of the chest, abdomen, pelvis, and any other involved disease sites (including brain MRI if appropriate) are to be obtained in all subjects (unless known anaphylaxis to contrast and/or medically contraindicated). If the use of IV contrast is medically contraindicated for a subject, 1 of the following options may be used (listed in order of preference): CT without contrast, MRI without contrast, or attempt to desensitize the subject with steroids. For each subject, the same imaging technique should be used throughout the study for tumor assessment. If a subject had brain lesions at study entry, brain MRI will be needed at all assessments. The timing of imaging is based on calendar time from the date of C1D1. Scans will be performed for all subjects at baseline and every 6 weeks for the first 6 months after C1D1 and then every 9 weeks thereafter until the occurrence of radiologic PD, as per RECIST 1.1, requiring discontinuation of treatment. Dose delays and cycle delays should not result in delays in the timing of imaging. For subjects with evidence of CR or PR, a confirmatory scan must be obtained at least 4 to 6 weeks after initial documentation of response CR or PR. Scans will be transferred to a central reader for collection and analysis by blinded independent central review (BICR).

Target and non-target lesions must be determined by the clinical site at baseline. Subjects who discontinue from treatment because of toxicity or clinical progression will continue to obtain radiologic response assessments at the protocol-required schedule until radiologic evidence of PD or initiation of new therapy, if clinically feasible. Additional CT or MRI studies may be performed at the discretion of the subject's treating physician to assess disease status, as medically indicated. Tumor response and progression will be determined using RECIST 1.1. For subjects who continue treatment despite radiologic evidence of PD as defined in Section 4.3.1, the subject will remain in the study and continue to be monitored according to the protocol required schedule of assessments ([Table 2](#)). The results of all imaging including those not specified as protocol assessments will be recorded on the eCRF.

Subjects who continue treatment following implementation of PA5 will be expected to have scans performed per standard of care, as indicated by local practice. Tumor response data will no longer be collected for this study; however, disease status should still be monitored by the treating physician to determine if progression has occurred, and whether the subject is continuing to derive clinical benefit.

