#### **4.3.1. Treatment After Progression**

Subjects will be treated until PD (according to RECIST 1.1 by Investigator's assessment), unacceptable toxicity, study withdrawal, or death, whichever comes first. However, treatment may be continued beyond PD if there is evidence of clinical benefit per the Investigator and the subject is tolerating study treatment. The following clinical criteria should be met for subjects to continue to receive treatment beyond the Investigator-assessed progression:

- Absence of symptoms and signs indicating clinically significant progression of disease.
- No decline in performance status.
- Absence of symptomatic rapid disease progression requiring urgent medical intervention (eg, symptomatic pleural effusion, spinal cord compression).

Sponsor consultation is required before subjects initiate the treatment beyond progression. If this occurs, the subject will remain in the study and continue to be monitored according to the protocol schedule of assessments ([Table 2](#)).

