#### **4.4. End of Treatment Visit**

The End of Treatment (EOT) Visit should be conducted within 30 days after the decision has been made to discontinue treatment. If this is scheduled for 30 days ( $\pm$  14 days) after the last dose, the results from these assessments may also be used for the 30-Day Safety Follow-up Visit. Subjects who discontinue treatment because of toxicity will continue with radiologic response assessments at the protocol-required schedule, until PD or initiation of new therapy with capture of radiologic evidence of PD if clinically feasible. The reason for treatment discontinuation will be documented and any treatment-related AEs or clinically significant abnormal laboratory values at that time will be followed until resolution or stabilization.

- Complete physical examination including weight.
- Blood samples for:

- CBC with differential.
- Serum chemistry panel and liver function tests, glucose, creatinine, BUN, total bilirubin, AST, ALT, alkaline phosphatase, serum albumin, sodium, potassium, calcium, chloride, bicarbonate, magnesium, and phosphorus.
- Urine pregnancy test.
- Tumor assessment: CT or MRI scan with IV contrast as appropriate (chest, abdomen, pelvis, and other regions of known/suspected involvement), unless known anaphylaxis to contrast or medically contraindicated as described in Section 9. If imaging was obtained within 2 weeks of the EOT Visit, imaging does not need to be repeated.
- Blood collection for PK and ADA serum samples.
- Blood collection for biomarker samples.
- Record AEs.
- Concomitant medications.
- **CCI**

For subjects continuing treatment following implementation of PA5, EOT assessments will be performed according to [Table 3](#).

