6. EFFICACY ANALYSES

Efficacy analyses will be performed primarily based on the Full Analysis Set and may be also performed for selected endpoints based on the Efficacy Evaluable Analysis Set.

For the purposes of analysis for tumor response-based endpoints including ORR, DCR (disease control rate), CBR, BOR, DOR and PFS, documented progression refers to progression based on radiologic assessment as determined by the investigator or central review (BICR), not clinical progression.

Tumor response-based endpoints, including ORR, DCR, CBR, DOR, and PFS will be analyzed based on both investigator reviewed and BICR results.

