Other anti-cancer treatment is initiated	Censored	Date of last adequate tumor assessment before starting other anti-cancer treatment
Other anti-cancer treatment is not initiated	Censored	Date of last adequate tumor assessment

Progression Free Survival (PFS)

PFS will be defined as the time from the date of first dose of study drug to the date of first documentation of disease progression by investigator assessment or BICR based on RECIST v1.1 or death due to any cause, whichever comes first. The censoring rules for PFS are specified in [Table 2](#).

Table 2. Censoring Rules for PFS

Case	Outcome	Date of Event/Censoring
No adequate response assessment after the first dose		
No baseline tumor assessment or alive	Censored	First dose date
Died prior to second scheduled disease assessment without initiation of other anti-cancer therapy	Event	Death date
Died immediately after ≥ 2 consecutive missed assessments or new anti-cancer therapy, if any	Censored	First dose Date
Continued scheduled response assessments until objective PD or death		
PD or death documented after ≤ 1 missed disease assessments, and before other anti-cancer therapy, if any	Event	PD or Death date, whichever occurs first
PD or death immediately after ≥ 2 consecutive missed disease assessments, or after other anti-cancer therapy, if any	Censored	Date of last adequate tumor assessment prior to the earlier date of ≥ 2 consecutive missed disease assessment and other anti-cancer therapy, if any
Continued scheduled response assessments without objective PD or death		
Other anticancer treatment is initiated	Censored	Date of last adequate tumor assessment before starting other anti-cancer treatment
Other anticancer treatment is not initiated	Censored	Date of last adequate response assessment

Overall Survival (OS)

OS will be measured from the date of first dose of study drug to death from any cause. Participants not known to have died are censored on the date they were last known to be alive.

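### BICR PFS can be informatively censored at investigator-called progression, and no readable analysis shows how much this matters

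*Protocol*

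**What the plan says.** **Who ends treatment and imaging.** Protocol Section 4.3.1: "Subjects will be treated until PD (according to RECIST 1.1 by Investigator's assessment), unacceptable toxicity, study withdrawal, or death, whichever comes first". Protocol Section 9 sets the scan interval as "every 6 weeks for the first 6 months after C1D1 and then every 9 weeks thereafter". The same section also fixes when protocol imaging ends, which is "until the occurrence of radiologic PD, as per RECIST 1.1, requiring discontinuation of treatment". No passage extends imaging until BICR agrees.

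**Exceptions.** For patients treated despite radiologic progression, Section 9 says "the subject will remain in the study and continue to be monitored according to the protocol required schedule of assessments". Section 9 also says "Subjects who discontinue from treatment because of toxicity or clinical progression will continue to obtain radiologic response assessments at the protocol-required schedule", until radiologic progression or new therapy, if clinically feasible. Section 4.4 is narrower: "Subjects who discontinue treatment because of toxicity will continue with radiologic response assessments at the protocol-required schedule, until PD or initiation of new therapy". The Methodology part of the Synopsis likewise names toxicity only.

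**What counts as an event.** SAP Section 6.2.1 ends PFS at "first documentation of disease progression by investigator assessment or BICR based on RECIST v1.1 or death due to any cause". SAP Section 6 adds that "documented progression refers to progression based on radiologic assessment as determined by the investigator or central review (BICR), not clinical progression". PFS is to be produced for both readers.

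**Censoring.** SAP Table 2 censors at the last adequate scan when progression or death comes after other anticancer therapy, or straight after two or more missed assessments in a row. Death after at most one missed assessment, and before other therapy, is an event. Protocol Section 11.2 censors only patients with neither progression nor death at cutoff or database lock. SAP Section 1 gives the SAP precedence.

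**Sensitivity analyses.** Protocol Section 11.2 repeats PFS in the Response Evaluable population, which leaves the censoring unchanged. SAP Section 6.2.2 names CBR and DCR, not PFS. The content of SAP Section 6.3 is redacted.

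**The concern.** Two readers are used, but only one of them controls when imaging stops. A patient whom the investigator calls progressed, and BICR does not, usually leaves the scan schedule at that visit. BICR then has no further scan on which to call progression, and Table 2 may also remove the later death. Kaplan-Meier estimation assumes that patients censored at a scan have the same future risk as those still followed. A patient just judged to be progressing plausibly has a higher risk.

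BICR PFS is a named secondary endpoint, and SAP Section 2.2 foresees regulatory, publication and conference use. With a single arm per cohort, no control group shares the distortion. At stake are the reported median and milestone rates. The primary ORR and type I error are not affected.

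**Working it through.** The documents give no expected PFS, event count or PFS power, so there is no planned figure to reproduce. I traced the rules and then sized the effect under stated assumptions.

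**1. Trace: investigator calls PD, BICR does not on that scan**

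| What happens next | BICR PFS under SAP Table 2 | Under Protocol 11.2 |
|---|---|---|
| Treated beyond PD, scans continue | BICR PD can still be observed | same |
| Stops; dies after at most 1 missed assessment, no new therapy | event at death | event at death |
| Stops; dies after 2 or more missed assessments | censored at last adequate scan | event at death |
| Starts new therapy; dies later | censored at last adequate scan before therapy | event at death |
| Stops; alive at cutoff | censored at last adequate scan | censored at last adequate scan |

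This reads scans not done after the stop as missed; Table 2 does not say so explicitly. The end-of-treatment scan in Protocol Section 4.4 may add one more image for some patients. It is not modelled and would reduce the effect.

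**2. Inputs**
- From the documents: scans at weeks 6, 12, 18 and 24, then 9-weekly. Reference median PFS is about 2.3 months for HNSCC and 2.7 to 3.8 months for SCLC, with 4 months in a later SCLC trial (Protocol Section 1.2).
- Assumed: exponential time to progression, median 4.0 months; median survival after progression 4.5 months; half of those who stop imaging start new therapy; a share f of 10%, 20% or 30% in which BICR would call PD one scan after the investigator.
- Plausibility of 4.5 months, using OS minus PFS (differences of medians are only indicative): HNSCC 5.1 − 2.3 = 2.8 to 6.9 − 2.3 = 4.6; SCLC 7.4 − 2.7 = 4.7 and 8.4 − 3.8 = 4.6.

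**3. How many later deaths are lost.** Two 6-week intervals are 12/(52/12) = 2.77 months. P(alive then) = 0.5^(2.77/4.5) = 0.65. Among discordant patients alive when imaging stops in the 6-weekly period, the share censored is therefore about 0.5 + 0.5 × 0.65 = 0.83. About 17% remain events through early death.

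**4. Control.** With f = 0, 6-month PFS is the survival at the last scan before month 6: week 24 = 5.54 months, and 0.5^(5.54/4) = 0.383. The simulation gives 38.4% under both rules, so the bias is zero.

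**5. Six-month BICR PFS (200,000 simulated patients per row)**

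| f | A: imaging continued to BICR PD | B: Table 2 | B − A | C: investigator PD counted | A − C | Censored under B |
|---|---|---|---|---|---|---|
| 10% | 39.2% | 41.6% | +2.4 | 38.3% | 0.9 | 7% |
| 20% | 40.0% | 45.1% | +5.1 | 38.2% | 1.8 | 14% |
| 30% | 40.9% | 48.9% | +8.0 | 38.3% | 2.6 | 21% |

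A second, separately coded version gives about +3, +6 and +9. If 25% are treated beyond progression (assumed), the figures are about +2, +4 and +6 to +7.

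The median is a poor gauge because it jumps between scans. A against B is 4.15 v 5.54 months at 10%, 5.22 v 5.54 at 20%, and 5.54 v 5.54 at 30%.

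**6. Loss of imaging before any radiologic PD** (scan not feasible, or new therapy started). This route touches both readers. With f = 0 and 10% or 20% lost after the scan before PD (assumed), 6-month PFS is 41.0% v 38.1% (+2.9) or 44.5% v 38.2% (+6.3). With f = 30% and 15% lost, BICR PFS is 52.8% v 40.5% (+12.3).

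**The case against.** **The case for leaving the plan alone.** PFS is secondary and descriptive, the POC stage has no hypothesis, and the minimum for expansion is a response count. Table 2 is a conventional rule set. Investigator PFS is reported beside BICR PFS and is immune to the discordance route, so a gap between them would be visible. The documents give no discordance rate. The proposed analysis largely moves BICR PFS towards investigator PFS. It would also count as an event a patient who stopped for toxicity and switched drug.

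Most of this limits the point without removing it. Investigator PFS is only a partial check. It shares the new-therapy censoring, and a gap between two curves does not show how many BICR censorings fell at investigator progression. Returning to the definition in Protocol Section 11.2 would not fully cure the problem either, because it dates the event at death.

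**Stronger readings that a reader might infer, and that the documents do not support**
- *BICR PFS can only err upward.* The direction depends on censored patients being at higher risk. The simulation builds that in, and the documents do not show it.
- *Every investigator progression ends imaging, and every later death is censored.* Treatment beyond progression and the early-death rule contradict this.
- *Patients with clinical progression are released from imaging.* Section 9 keeps them on schedule if feasible. Only those who cannot be scanned or who start new therapy are lost. What does stand is that the Synopsis and Section 4.4 name toxicity only.
- *All cohorts will be read against a 2-4 month benchmark.* Background PFS is given for HNSCC and SCLC only, and no formal comparison is planned.
- *The SAP contains no check at all.* With Section 6.3 redacted, absence can be claimed for the readable text only.

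**Conclusion.** The point holds in qualified form. The imaging stop rule and Table 2 together allow BICR PFS to be censored at investigator-called progression, and the SAP censors deaths that the protocol's own PFS definition would count. No readable passage varies the PFS censoring, tabulates its reasons or reports reader concordance on progression.

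Under the assumptions above, 6-month BICR PFS is overstated by roughly 2 to 9 percentage points for 10-30% discordance. The upper end is larger if patients also leave imaging before radiologic progression. Discordance and drop-out are assumed throughout, and the effect is zero if the censoring is uninformative. Investigator PFS is exposed only through new therapy or imaging that is not feasible. This is a worthwhile, inexpensive improvement to a secondary endpoint. It does not challenge the primary analysis.

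**What to change.** Keep Table 2 as the main analysis. In SAP Section 6.2.2, add one pre-specified PFS sensitivity analysis per reader:

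- **BICR:** count investigator PD as an event, at its date, when BICR has no PD and no later scan exists.
- **Both readers:** count the start of new anticancer therapy, and clinical progression where recorded, as events. Do not censor deaths because of missed assessments.
- **Report by cohort:** the number censored for each reason, and investigator-BICR concordance on PD.
- **Clarify in Table 2:** whether scans no longer required after imaging stops count as missed.

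Separately, reconcile Protocol Section 9 (imaging continues after toxicity or clinical progression) with the Synopsis and Section 4.4 (toxicity only).

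**Cost.** One table per cohort, from data that are largely collected already: all imaging results (Section 9), reasons for stopping treatment (Section 4.4), and subsequent therapy up to Amendment 5 (Section 4.7). The discontinuation reasons in Section 4.6 do not separate clinical from radiologic progression and the case report form is not visible, hence the qualifier on clinical progression. The estimate will be somewhat pessimistic, for example for patients who switch therapy after toxicity. In the runs above, which have no such switchers, it fell 0.9 to 2.6 points below continued imaging, so read it with Table 2 as a range.

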## 10. ASSESSMENT OF SAFETY

### 10.1. Safety Parameters

#### 10.1.1. Clinical Laboratory Investigations

All clinical laboratory samples for safety will be collected and analyzed by the site's local laboratory with appropriate clinical action taken based on the Investigator's clinical judgment. All investigations will be assessed for all subjects at Screening, during treatment, and upon treatment discontinuation per the schedule of assessments ([Table 2](#)). Clinical laboratory samples will also be collected at the 30-Day Safety Follow-up Visit. Additional and more frequent tests may be performed at the Investigator's discretion. The specific details of each assessment will be recorded on the appropriate eCRF. In the event of clinically significant abnormal results, tests should be repeated within 24 to 48 hours to confirm abnormality. Results for these laboratory tests should be followed until resolution. The panels of laboratory tests to be performed are shown below:

**Hematology:** hemoglobin, white blood cell (WBC) count and differential (with ANC), and platelet count.

**Clinical Chemistry:** total protein, albumin, total bilirubin, alkaline phosphatase (ALP), ALT, AST, creatinine (see [Appendix 17.3](#)) and clinical chemistries including glucose, sodium, potassium, magnesium, chloride, bicarbonate ( $\text{CO}_2/\text{HCO}_3^-$ ), calcium, phosphorus.

**Urinalysis:** performed locally on a freshly voided clean sample by dipstick for protein, glucose, blood, pH, and ketones. If dipstick findings are abnormal based on the Investigator's judgment, then a microscopic evaluation will be performed to assess the abnormal findings. Urinalysis will be performed at Screening only and as clinically indicated with details regarding casts, WBC count and RBC count, and bacteria recorded. Only abnormal results will be captured on the eCRF.

**Pregnancy and FSH Testing:** Female subjects of childbearing potential must have a negative serum or urine pregnancy test result within 72 hours prior to administration of the first dose of study drug and a negative urine pregnancy test result of Day 1 of every cycle while on study drug. If the urine test is positive or cannot be confirmed as negative, a serum pregnancy test will be required. Serum FSH testing will be conducted as needed per [Appendix 17.5](#) for determination of childbearing potential.

**LDH and Uric Acid:** will only be required at Screening. May be obtained more frequently at the discretion of the treating physician if abnormal results warrant follow-up. Results of unscheduled tests should be documented.

